2.7.3 Inferential Analysis for the Safety Analysis

A Fisher's exact test will be provided to compare the AE rates for MV-CHIK vs. Priorix®. P-values will also be provided to compare AE rates between treatment groups (pairwise comparisons). No adjustment for multiple testing will be performed.

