Group M2: Priorix® on study day -28, placebo on day 0 and 28 and MV-CHIK high dose on day 168 and 196

All subjects of treatment group A, B, C and D will receive three i.m. injections (on study day 0, 28 and 196). Subjects of group A and B will receive MV-CHIK low dose or control vaccine Priorix® and subjects of group C and D will be treated with MV-CHIK high dose or the control-vaccine Priorix®. All subjects of group A, B, C and D additionally will be randomized to one of two treatment sequences: group A and C will receive MV-CHIK or control-vaccine on study day 0 and 28, followed by placebo (saline) on day 196, and group B and D receive placebo on study day 0 and MV-CHIK or Priorix® on day 28, followed by an additional vaccination of the same product on day 196 (boosting vaccination).

All subjects of the measles booster group M1 and M2 will receive five i.m. injections on study day -28, 0, 28, 168 and 196. The first vaccination will be Priorix® (or equivalent measles vaccine) on study day -28. Group M1 will receive MV-CHIK high dose vaccinations on day 0 and day 28 and placebo on day 168 and 196. Group M2 will receive placebo on day 0 and 28 and MV-CHIK high dose on day 168 and on day 196.

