### 13.2 Safety Analysis

Solicited AEs (reactogenicity): Solicited local and solicited systemic AEs will be summarized for the 7 day period, by AE grade (mild, moderate, severe), by group and by dose. Solicited AEs will not be coded into MedDRA or assessed for relatedness. The number and percentage of subjects with AEs will be presented. Subjects who reported data for a solicited event at any time point during the time period summarized would be included in the denominator for that event. Thus, denominators for each solicited event will not include subjects who were missing all data for that event, during the time period summarized. P-values for AE rates for MV-CHIK vs. Priorix® (or equal control-vaccine), for the same schedule, will be provided in summary tables (pairwise comparisons).

Unsolicited AEs: Separately, the number and percentage of subjects with unsolicited treatment emergent adverse events (TEAEs), medically-attended AEs (MAEs) and serious adverse events (SAEs) will be presented for each treatment group overall and by system organ class/preferred term, and by AE grade, and relatedness. All SAEs and MAEs are also included in TEAE tables. Arthritis AEs, AEs of special interest (AESI), will be included in the TEAE tables. For unsolicited AEs, all subjects entered into the study who receive at least one vaccination will be included in the safety analysis based on the product received (“as treated”), for the time period summarized. P-values for AE rates for MV-CHIK vs. Priorix®, for the same schedule, will be provided in summary tables (pairwise comparisons).

Unsolicited AEs and concomitant diseases will be coded using the MedDRA coding dictionary; concomitant medications will be coded using the WHO Drug Dictionary.

Solicited and unsolicited AEs (local and systemic), MAE, SAE and AESI (arthralgia) will be recorded up to Visit 6 (day 224).

Safety analyses will be performed by means of descriptive measures. Laboratory values will be assigned a grade. Changes in laboratory values and grades as well as vital signs from study entry to end of treatment/follow up will be analyzed descriptively.

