## 14.5 Collection, Recording and Reporting of Adverse Events

All events meeting the definition of an Adverse Event must be collected and reported starting with randomization (Visit 0/ day -28) until the end of the protocol required post-treatment follow-up period (Visit 6 28 days after the last vaccination).

At each contact to the site (visit or telephone, excluding safety visits) where the subject is not seeing the investigator or his staff (e.g. visits to the laboratory), the subject must be asked about adverse events. All adverse events either observed by the investigator or reported by the subject must be recorded by the investigator and evaluated.

The subjects will be asked in general: "How are you?" as well as specifically: "Have you experienced any problems since the last contact?"

The investigator should record the diagnosis, if available. If no diagnosis is available, the investigator should record each sign and symptom as individual adverse events.

The investigator must record all adverse events in the eCRF. One single adverse event line must be used per adverse event, from start to resolution. For serious adverse events, the Serious Adverse Event Report Form must also be completed.

The investigator must report all SAEs with the completed SAE Report Form within 24 hours after learning of its occurrence to:

Assign Safety Desk: [contact]

Email: [[contact]](mailto:[contact])

For urgent questions please call the 24-hours Safety [contact]**

Under certain circumstances the first notification can be done by phone; nevertheless, a written Serious Adverse Event Report Form has to be submitted for confirmation to Assign Safety Desk. Reporting timelines are applicable also if the SAE is not felt to be treatment-related. The monitor must be informed accordingly.

The original copy of the SAE Report Form and the fax confirmation sheet must be kept with the documentation at the study site.

Please note: Each SAE has also to be documented in the eCRF as a serious adverse event in the corresponding AE section.

The sponsor is responsible to fulfill the requirements of expedited reporting of all SUSARs (Suspected Unexpected Serious Adverse Reaction) to the Competent Authorities, Ethics Committees and principal investigators concerned according to national and European law and regulations.

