2.13 Local/systemic tolerability symptoms (diary evaluation)

Local/systemic tolerability symptoms will be recorded by the study subjects at each diary day and diary period (for a period of 7 consecutive days after each vaccination).

Diary periods are defined as follows:

- 2. diary period 1 is after vaccination 1 (on Visit 0; only for measles booster group M1 and M2)
- 3. diary period 2 is after vaccination 2 (on Visit 1 Day 0)
- 4. diary period 3 is after vaccination 3 (on Visit 2 Day 28)
- 5. diary period 4 is after vaccination 4 (on Visit 4 Day 168; only for measles booster group M1 and M2)
- 6. diary period 5 is after vaccination 5 (on Visit 5 Day 196)

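### The SAP's pairwise AE tests set M1/M2 (five injections, 252 days) against groups with three injections and 224 days, so M versus non-M p-values lean towards more AEs in M

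*SAP*

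**What the plan says.** **Exposure.** The protocol synopsis gives two injection schedules: "All subjects of treatment group A, B, C and D will receive three i.m. injections (on study day 0, 28 and 196", and "All subjects of the measles booster group M1 and M2 will receive five i.m. injections on study day -28, 0, 28, 168 and 196". The control-vaccine subjects sit inside groups A-D and follow the three-injection schedule. SAP 2.13 marks two of the five diary periods as belonging to the M groups alone: "diary period 1 is after vaccination 1 (on Visit 0; only for measles booster group M1 and M2" and "diary period 4 is after vaccination 4 (on Visit 4 Day 168; only for measles booster group M1 and M2". Protocol 14.5 says that adverse events are "collected and reported starting with randomization (Visit 0/ day -28) until the end of the protocol required post-treatment follow-up period". For A-D, Visit 0 and Visit 1 fall together on Day 0.

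**Tests.** SAP 2.7.3 provides Fisher's exact test for MV-CHIK vs Priorix and adds: "P-values will also be provided to compare AE rates between treatment groups (pairwise comparisons". No multiplicity adjustment is made. SAP 8.3 refers to 2.7.3 and lists tables of subjects with one or more events, by treatment group. It counts an event as treatment-emergent if it starts on or after the first vaccination, and sets no end date or per-injection window. The preliminary analysis takes events starting up to Visit 3. SAP 2.3 lists eight groups (CV1, CV2, A, B, C, D, M1, M2), merges Austrian low dose and German high dose within each M group, and includes M1/M2 in the MV-CHIK total column.

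**The protocol's limit.** Protocol 13.2 says: "P-values for AE rates for MV-CHIK vs. Priorix®, for the same schedule, will be provided in summary tables (pairwise comparisons". SAP 2.7.3 does not repeat the schedule condition, while SAP 2.17 states that the analysis planned in the protocol is not being changed.

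**The concern.** The proportion of subjects with at least one event rises with the number of injections and with the time observed. Two of the five diary periods, and the first four weeks of AE collection, exist only for M1/M2. A pairwise test of an M group against any other group therefore mixes the effect of the vaccine with the effect of more injections and more observation. Crediting each event to the right product does not cure this, because the rate itself is formed over unequal opportunity.

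At stake is the reading of the M-group safety tables. A small p-value against A or C could be taken as a sign that MV-CHIK is worse tolerated after a recent measles vaccination when nothing of the kind is true. The protocol's same-schedule limit would have kept M1/M2 out of the MV-CHIK vs Priorix test, since no control group follows their schedule. The SAP drops that protection without recording a change.

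**Working it through.** **1. Windows, checked against the protocol's own durations.** Protocol 8.4 gives about 231 days for A-D and about 259 for M1/M2, including up to 7 days of screening.
- A-D: 7 + 224 = 231.
- M1/M2: 7 + 28 + 224 = 259.

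Both are reproduced. Without screening, AE collection is 224 days (Day 0 to 224) and 252 days (Day -28 to 224), a ratio of 252/224 = 1.125. Diary days are 3 × 7 = 21 and 5 × 7 = 35.

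**2. Which comparisons are affected.** Eight groups make 8 × 7 / 2 = 28 pairs. M1 and M2 against the six others make 2 × 6 = 12 affected pairs. The other 16, which include M1 vs M2, are unaffected.

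**3. Solicited AEs, final analysis.** The per-injection risks are assumptions, treated as independent between injections. The rate is 1 minus the product of (1 − risk) over injections. A receives two MV-CHIK and one placebo; M1 receives one Priorix, two MV-CHIK and two placebo. Group sizes are 60 and 20 (Protocol 6.3). False rejection is the exact probability that a two-sided Fisher test at 0.05 rejects.

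| Assumed risk: MV-CHIK / Priorix / placebo | A | M1 | Excess (points) | False rejection |
|---|---|---|---|---|
| 30 / 10 / 5% | 53.5% | 60.2% | 7 | 6% |
| 30 / 20 / 10% | 55.9% | 68.2% | 12 | 13% |
| 20 / 15 / 10% | 42.4% | 55.9% | 14 | 14% |
| 10% for all | 27.1% | 41.0% | 14 | 17% |
| 20% for all | 48.8% | 67.2% | 18 | 26% |
| 30% for all | 65.7% | 83.2% | 17 | 27% |

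Worked example, row 2: A = 1 − 0.7² × 0.9 = 0.559; M1 = 1 − 0.8 × 0.7² × 0.9² = 0.682. With equal rates in both groups the same test rejects about 3.5% of the time.

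Correlation between injections within a subject lowers the excess. With beta-distributed subject risk (mean 10-50%, correlation 0.1 to 0.5) and the same risk for every injection, it is 4 to 15 points.

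**4. Unsolicited AEs.** Assume a constant hazard, so the M rate is 1 − (1 − q)^r, where q is the A rate over the same analysis. At the final analysis r = 1.125. At the preliminary analysis r = 84/56 = 1.5 (Day -28 to 56 against Day 0 to 56).

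| q in A | M, final | False rejection, final | M, preliminary | False rejection, preliminary |
|---|---|---|---|---|
| 30% | 33.1% | 4.2% | 41.4% | 12% |
| 50% | 54.1% | 4.6% | 64.6% | 17% |
| 66.7% | 71.0% | 4.5% | 80.8% | 18% |

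The 66.7% is the Phase 1 unsolicited rate in Protocol 2.4, used only as an illustration. The preliminary figures use the full planned 20 vs 60. SAP 2.2.1 moved that analysis ahead of complete Visit 3 data, so the actual numbers could be smaller.

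**5. MV-CHIK total column.** The total is (240 × A-D rate + 40 × M rate) / 280. At equal per-injection risks of 10/20/30% the inflation is 2.0/2.6/2.5 points. Fisher's test of 280 vs 40 rejects 4.3/5.1/5.6% of the time, against 3.8/4.1/4.1% with equal windows.

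**The case against.** The strongest reply is that little depends on these p-values. Protocol 13.2 calls the safety analysis descriptive, the tests are unadjusted, and no decision rule uses an M vs A-D comparison. SAP Tables 4.29, 4.31, 4.33, 4.35, 4.38, 4.40, 4.42 and 4.44 already show diary symptoms by period, so a reader of the final report can set M1 periods 2 and 3 beside A or C. All of this stands, and it limits the harm. But those tables carry no test and are not produced for the preliminary analysis, while the tests that are planned use the unmatched rates.

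A second reply is that the SAP never says its rates cover the whole study. That is true. Solicited events are summarised over 7 days, without saying after which injection, and the endpoint list keeps a 28-day post-vaccination AE rate. The whole-study reading follows from the treatment-emergent definition and from tables that name no period. The window is left open rather than stated wrongly, but the SAP offers no other for the final analysis.

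Four stronger readings may tempt a reader, and the documents support none of them:
- That M1/M2 exist to test tolerability after a measles boost. Protocol 2.5 and 4.1.2 give them an immunogenicity purpose.
- That 17-27% is the expected error. It requires Priorix and saline to be as reactogenic as MV-CHIK, so it is an upper range.
- That the extra 28 days distort unsolicited tests at the final analysis. They barely move them.
- That the MV-CHIK total is seriously inflated. Two to three points does not justify removing M1/M2 from a descriptive column.

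Finally, matched windows alone would not make M1 fully comparable with A or C. SAP 2.3 pools two doses, and subjects and staff know who is in an M group. The dose problem can be handled in the presentation; the lack of blinding to M membership cannot.

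**Conclusion.** The point holds, within limits. As written, SAP 2.7.3 and 8.3 give p-values for 12 of 28 group pairs that are biased towards more AEs in M1/M2. The other 16 pairs are sound. The direction follows from the schedules; the size depends on per-injection risks that the documents do not give.

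For solicited AEs, a plausible range for M1 vs A is 6-14% false rejection, with 17-27% as the equal-risk upper range, against about 3.5% when windows match. For unsolicited AEs the bias is about 3-4 points and immaterial to the test at the final analysis. It is 11-15 points, with 12-18% false rejection, at the preliminary analysis, under a constant hazard and planned group sizes. The effect on the MV-CHIK total is minor.

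The loss of the same-schedule limit is a plain discrepancy between protocol and SAP and needs no assumption. This concerns secondary safety inference and does not touch the primary immunogenicity result, but the correction is cheap enough that it should be made.

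**What to change.** In SAP 2.7.3 and 8.3:
- Test M1 or M2 against other groups only on matched windows. For solicited AEs, attach the tests to the diary periods already tabulated: M1 periods 2-3, or M2 periods 4-5, against A/C periods 2-3. For unsolicited AEs, use matched post-injection windows, in both the preliminary and the final analysis.
- Present these comparisons by M-group dose: Austrian low-dose subjects against A, German high-dose subjects against C.
- Restore the same-schedule limit for MV-CHIK vs Priorix: A and C vs CV1, B and D vs CV2. M1/M2 then drop out of that test.
- Report whole-study M rates, and the MV-CHIK total column, descriptively without a p-value.
- State in one sentence that M membership is known to subjects and staff, as a remaining limit on these comparisons.

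The cost is SAP wording and reprogramming of existing tables, with no new data. The drawback is fewer events and small dose subgroups in the M comparisons, so they will have little power and are best read as estimates with intervals.

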2.8 Center and Country Effect

This study is a multicentre study and conducted in three Austrian and one German site.

As the M1 an M2 dose is different in both countries (cp. Section 1.2) a stratification by countries will be prepared only for listings. No stratification by centers inside the country will be done.

2.9 Drop-outs

If "early termination" was ticked on the eCRF page "Study end page" the subjects was considered as early termination. If the study was terminated early a reason has to be indicated (i.e. subject withdrew consent, protocol, deviation, adverse event, failure to comply with protocol requirements, lost to follow-up, discretion of the investigator or other reason).

2.10 Screening Failures

All subjects who signed the informed consent were registered in the eCRF. If the question "Is subject eligible for the study" was answered with "no" or the question "Has the subject been randomized" was answered with "no", the subject was considered a screening failure.

2.11 Handling Missing Data

In general, missing data will not be imputed. However, for adverse events missing assessments for severity, causality and seriousness will be imputed with the worst case (severity=severe, causality=definitely and seriousness=yes).

2.13 Local/systemic tolerability symptoms (diary evaluation)

Local/systemic tolerability symptoms will be recorded by the study subjects at each diary day and diary period (for a period of 7 consecutive days after each vaccination).

Diary periods are defined as follows:

- 2. diary period 1 is after vaccination 1 (on Visit 0; only for measles booster group M1 and M2)
- 3. diary period 2 is after vaccination 2 (on Visit 1 Day 0)
- 4. diary period 3 is after vaccination 3 (on Visit 2 Day 28)
- 5. diary period 4 is after vaccination 4 (on Visit 4 Day 168; only for measles booster group M1 and M2)
- 6. diary period 5 is after vaccination 5 (on Visit 5 Day 196)

2.13.1 Local tolerability symptoms

- Symptoms: injection side pain (pain without touching), tenderness (pain upon touching), itching (pruritus), redness (erythema), hardening (induration) and swelling (edema)
- If symptoms are present, the investigator interprets the subject entries:
 - (mild/moderate/severe) for injection side pain (pain without touching), tenderness (pain upon touching) and itching (pruritus) as grade 1 (mild), grade 2 (moderate), grade 3 (severe) or grade 4 (potentially life threatening).
 - circle A to circle E) for redness (erythema), swelling (edema) and hardening (induration) as grade
 1, grade 2 grade 3 or grade 4.

2.13.2 Systemic tolerability symptoms

- Symptoms: headache, body temperature (fever), joint pain (arthralgia), flu-like symptoms, nausea, vomiting, rash, limb discomfort, myalgia and excessive fatigue
- If symptoms are present, the investigator interprets the subject entries:
 - (mild/moderate/severe) for headache, muscle pain, joint pain (arthralgia), flu-like symptoms, nausea, vomiting, rash, vomiting and excessive fatigue as grade 1 (mild), grade 2 (moderate), grade 3 (severe) or grade 4 (potentially life threatening).
 - (°C) for body temperature (fever) as grade 1, grade 2, grade 3 or grade 4.

For summarizing local/systemic severity symptoms the outcome is set to the worst severity. The order for severity is grade 1 to grade 4, where grade 4 is the worst severity.

2.14 Protocol Deviations

Protocol deviations will be collected only for the final analysis from the study database. The listing of protocol deviations will be prepared by Assign Data Management and Biostatistics GmbH using information from the eCRF documentation as well as from monitoring.

Protocol deviations will be identified during a Blind Data Review Meeting (BDRM) attended by Assign Data Management and Biostatistics GmbH and Themis Bioscience GmbH (sponsor).

SAP (MV-CHIK-202, FINAL 3.0, 09-May-2018) Page 19 of 47 Based on: STAT03_A Statistical Analysis Plan Version 5.0, Effective Date 16-Dec-2016 Confidential and intellectual property of Assign DMB. No part of this document or its contents may be duplicated, referenced, published or otherwise disclosed in any form or by any means without prior written consent of Assign DMB.

The BDRM will take place after all outstanding queries have been resolved. Protocol deviations will be classified into major or minor protocol deviations based on their possible impact to the study results. Protocol deviations are defined as "major" if they are likely to affect the outcome of the study (e.g. effect on target variables). During the course of the study unforeseen events may occur or new scientific knowledge may become available, therefore final decisions on all protocol deviations for this analysis will be made on a case by case decision in the BDRM.

Subjects with major protocol deviations will be part of the Safety Population and mITT Population, but not part of the Per-Protocol Population (PP Population). Minor protocol violations will be regarded as fully evaluable and, therefore, will be part of the PP Population.

2.15 Medical Coding

Adverse events and medical history will be coded using MedDRA. Concomitant medications will be coded using WHO Drug Dictionary. Coding will be reviewed internally for consistency and will be approved by the sponsor prior to database snapshot and prior to database closure. For details to medical coding and the used coding dictionary versions, please refer to the Coding Guideline in DMP (Appendix 8; Version: Final 2.0; 05-May-2017).

2.16 Analysis Populations

Three analysis populations will be used in this analysis:

• Modified Intent-to-Treat (mITT) Population

The exploratory immunogenicity analyses will be based on the modified ITT population. The modified Intent-to-treat (mITT) analysis population is defined to include all subjects randomized who receive at least one vaccination. Subjects will be analyzed according to the treatment group to which they are randomized to, rather than by the actual treatment they received.

• Safety Population (Final Analysis only)

All safety analyses will be based on the Safety population, which is defined to include all subjects who entered into the study and receive at least one vaccination. All analysis based on the Safety population will be carried out using the actual treatment received.

• Per-Protocol (PP) Population (Final Analysis only)

The Per-Protocol population is defined as mITT population excluding those subjects with at least one major protocol deviation. The PP population will exclude an enrolled subject if one of the following criteria is met:

- Immunosuppressive drugs: Use of corticosteroids (excluding topical preparations) or immunosuppressive drugs within 30 days prior to vaccination, or anticipated use during the trial.
- Subjects with any confirmed immunosuppressive or immunodeficient condition, including human immunodeficiency virus (HIV), hepatitis A, B or C infection or a family history of congenital or hereditary immunodeficiency
- Subjects who received the wrong or no study medication
- Subjects with other major protocol deviations

SAP (MV-CHIK-202, FINAL 3.0, 09-May-2018) Based on: STAT03_A Statistical Analysis Plan Version 5.0, Effective Date 16-Dec-2016 Confidential and intellectual property of Assign DMB. No part of this document of Page 20 of 47

These criteria for potential protocol violation were identified at the time of planning the study. However, during the course of the trial unforeseen events may occur or new scientific knowledge may become available, therefore final decisions on whether any protocol violation could impact immune response and thus lead to exclusion from the PP population will be made by the sponsor on a case by case basis in a data review meeting. Sample testing issues may also lead to exclusion from the PP population for particular time points.

Changes in the Conduct of the Study or Planned Analysis 2.17

The statistical analysis plan is based on the final study protocols for Austria (Version 1.5; 24-Nov-2016) and Germany (Version 1.6; 19-Apr-2017). No changes in the conduct of the planned analysis as described in the CSP are intended.

However, the time point of the Preliminary Analysis was moved forward to August 2017. The Preliminary Analysis was initially planned to take place after all subjects completed Visit 3.

Page 21 of 47

3. **OVERALL STUDY INFORMATION**

Treatment groups for the preliminary analysis as well the final analysis are defined in section 2.3. Overall study information analysis will be prepared for the:

- Preliminary analysis: mITT population. •
- Final analysis: Safety, mITT and PP population. •

